### **4.3. Lifestyle Guidelines**

In this study, male patients who are able to father children and female patients who are of childbearing potential will receive PF-06840003, a compound for which the teratogenic risk is currently unknown. Two (2) methods of highly effective contraception must be used throughout the study and continued for at least 28 days after the last dose. The investigator or his or her designee, in consultation with the patient, will confirm the patient has selected two appropriate methods of contraception for the individual patient and his/her partner from the list of permitted contraception methods (see below) and will confirm the patient has been instructed in their consistent and correct use. Patients need to affirm that they meet the criteria for correct use of at least 2 of the selected methods of contraception. The investigator or his or her designee will discuss with the patient the need to use highly effective contraception consistently and correctly according to the schedule of activities and document such conversation in the patient's chart. In addition, the investigator or his or her designee will instruct the patient to call immediately if a selected contraception method is discontinued or if pregnancy is known or suspected in the patient or the patient's partner.

Highly effective methods of contraception are those that, alone or in combination, result in a failure rate of less than 1% per year when used consistently and correctly (ie, perfect use) and include the following:

1. Established use of oral, inserted, injected, implanted or transdermal hormonal methods of contraception is allowed provided the patient plans to remain on the same treatment throughout the entire study and has been using that hormonal contraceptive for an adequate period of time to ensure effectiveness.
2. Correctly placed copper-containing intrauterine device (IUD).
3. Male condom or female condom used WITH a spermicide (ie, foam, gel, film, cream, or suppository). For countries where spermicide is not available or condom plus spermicide is not accepted as highly effective contraception, this option is not appropriate.
4. Male sterilization with absence of sperm in the post vasectomy ejaculate.
5. Bilateral tubal ligation or bilateral salpingectomy or bilateral tubal occlusive procedure (provided that occlusion has been confirmed in accordance with the device's label).

6. Female partner who meets the criteria for non-childbearing potential, defined as:
- Have undergone a documented hysterectomy and/or bilateral oophorectomy;
  - Have medically confirmed ovarian failure; or
  - Achieved postmenopausal status, defined as follows: cessation of regular menses for at least 12 consecutive months with no alternative pathological or physiological cause; and have a serum follicle-stimulating hormone (FSH) level within the laboratory's reference range for postmenopausal women.

#### **4.4. Sponsor's Qualified Medical Personnel**

The contact information for the sponsor's appropriately qualified medical personnel for the study is documented in the study contact list located in the supporting study documentation.

To facilitate access to appropriately qualified medical personnel on study-related medical questions or problems, patients are provided with a contact card. The contact card contains, at a minimum, protocol and investigational compound identifiers, patient study numbers, contact information for the investigational site, and contact details for a contact center in the event that the investigational site staff cannot be reached to provide advice on a medical question or problem originating from another healthcare professional not involved in the patient's participation in the study. The contact number can also be used by investigational staff if they are seeking advice on medical questions or problems; however, it should be used only in the event that the established communication pathways between the investigational site and the study team are not available. It is therefore intended to augment, but not replace, the established communication pathways between the investigational site and the study team for advice on medical questions or problems that may arise during the study. The contact number is not intended for use by the patient directly, and if a patient calls that number, he or she will be directed back to the investigational site.

#### **4.5. Rater Qualifications**

Site staff (eg, physicians, nurses, psychologists, social workers, coordinators and research assistants) must be trained on the administration of the C-SSRS form prior to completing the first assessment. Completion of the necessary training will be documented in a training certificate.

Prior to implementation of the cognitive assessments in Part 2, site staff must also be trained on the administration of the COWA and HVLT-R. Completion of the necessary training will be documented in a training certificate.

### **5. STUDY TREATMENTS**

For the purposes of this study, and per International Conference on Harmonisation (ICH) guidelines investigational product is defined as a pharmaceutical form of an active ingredient or placebo being tested or used as a reference in a clinical trial, including a product with a marketing authorization when used or assembled (formulated or packaged) in a way different

from the approved form, or when used for an unapproved indication, or when used to gain further information about an approved use (ICH E6 1.33).

### **5.1. Allocation to Treatment**

Dose level allocation will be performed by the sponsor after patients have given their written informed consent and have completed the necessary screening assessments. Registration should occur before any other Day 1 activities are performed and preferably no more than 3 business days before Day 1. The site staff will email a complete Patient Enrollment Form to the designated sponsor study team member. The sponsor will assign a patient enrollment number and this email to the site.

No patient shall receive investigational product until the investigator or designee has received the following information in writing from the sponsor:

- confirmation of the patient's enrollment;
- specification of the dose level for that patient and
- permission to proceed with dosing the patient;

### **5.2. Patient Compliance**

Patients will be required to return all unused study treatment at the beginning of each cycle. The number of tablets returned by the patient at the end of the cycle will be counted, documented, and recorded for drug accountability. Treatment compliance (reported as a percent) will be defined as the number of tablets taken during the study divided by the expected number of tablets multiplied by 100%. Tablets that are not returned will be considered to have been taken unless reported otherwise by the patient. Drug diary records will be provided to the patients as an aid for the recording of study treatment compliance. Patients with a less than 75% compliance with the study requirements, for reasons other than toxicity, may be withdrawn from the study.

### **5.3. Investigational Product Supplies**

#### **5.3.1. Dosage Form(s) and Packaging**

PF-06840003 will be provided as tablets for oral administration. The 125 mg or 25 mg tablets will be supplied in high-density polyethylene (HDPE) bottles and labeled according to local regulatory requirements.

#### **5.3.2. Preparation and Dispensing**

The study treatment should be dispensed at each visit per the [schedule of activities](#). A qualified staff member will dispense the investigational product in the bottles provided, in quantities appropriate for the study visit schedule. The patient should be instructed to maintain the product in the bottle provided throughout the course of dosing and return the bottle to the site at the next study visit where accountability is to be performed.

See the Investigational Product manual for instructions on investigational product dispensation for administration. Investigational product should be dispensed by an appropriately qualified and experienced member of the study staff (eg, physician, nurse, physician's assistant, practitioner, pharmacist, or medical assistant) as allowed by local, state, and institutional guidance.

#### **5.4. Administration**

On days when patients have clinic visits where PK assessments are to be obtained, PF-06840003 should not be taken prior to the study visit. Daily oral dosing with PF-06840003 will be initiated on Cycle 1 Day 1 and should continue until end of treatment. The PF-06840003 can be taken after the study procedures required for that visit have been performed. Patients will be instructed to swallow the investigational product whole, and to not manipulate or chew the investigational product prior to swallowing.

PF-06840003 will be administered orally on an empty stomach (ie, no food or beverages other than water for two hours before or two hours after dosing) without adjustment for body size. Tablets should be administered with approximately 240 mL of ambient temperature water. Patients should be instructed to take their medication at approximately the same time each day and to not take more than the prescribed dose at any time. Patients who are assigned to a BID dosing regimen should be instructed to take their PF-06840003 every 12 hours  $\pm$  1 hour.

If a patient assigned to take PF-06840003 one time per day misses a day of treatment, he/she must be instructed not to "make it up" but to resume subsequent doses the next day as prescribed.

If a patient assigned to take PF-06840003 two times per day misses a dose by more than 4 hours of when they should have taken it, he/she must be instructed not to "make it up" but to resume subsequent doses at the next scheduled dosing time as prescribed.

If a patient vomits any time after taking a dose, he/she must be instructed not to "make it up" but to resume subsequent doses the next day as prescribed. If a patient inadvertently takes 1 extra dose during a day, the patient should not take the next dose of PF-06840003.

##### **5.4.1. Recommended Dose Modifications**

Every effort should be made to administer investigational product on the planned dose and schedule.

In the event of significant toxicity, dosing may be delayed and/or reduced as described below. In the event of multiple toxicities, dose modification should be based on the worst toxicity observed. Patients are to be instructed to notify investigators at the first occurrence of any adverse symptom.

Dose modifications may occur in one of three ways:

- Within a cycle: dosing interruption until adequate recovery and dose reduction, if required, during a given treatment cycle;
- Between cycles: next cycle administration may be delayed due to persisting toxicity when a new cycle is due to start;
- In the next cycle: dose reduction may be required in the current and/or subsequent cycle based on toxicity experienced in the current/previous cycle.

#### **5.4.2. Dosing Interruptions**

Patients experiencing the following adverse events should have their treatment interrupted:

- Grade 3 or 4 potentially treatment related toxicity;
- Intolerable Grade 2 toxicity despite supportive care.

Appropriate follow up assessments should be done until adequate recovery occurs as assessed by the investigator. Criteria required before treatment can resume are described in [Section 5.4.3 Dose Delays](#).

Doses may be held as needed until toxicity resolution. Depending on when the AE resolved, a treatment interruption may lead to the patient missing all subsequent planned doses within that same cycle or even to delay the initiation of the subsequent cycle.

If the AE that led to the treatment interruption recovers within the same cycle, then re-dosing in that cycle is allowed. Doses omitted for toxicity are not replaced within the same cycle. The need for a dose reduction at the time of treatment resumption should be based on the criteria defined in section [Dose Reductions](#), unless expressly agreed otherwise following discussion between the investigator and the sponsor.

In the event of a treatment interruption for reasons other than treatment-related toxicity (eg, elective surgery) lasting >4 weeks, treatment resumption will be decided in consultation with the sponsor.

#### **5.4.3. Dose Delays**

Re-treatment following treatment interruption for treatment-related toxicity or at the start of any new cycle may not occur until all of the following parameters have been met:

- ANC  $\geq 1,000/\text{mm}^3$ .
- Platelet count  $\geq 50,000/\text{mm}^3$ .
- Non-hematologic toxicities have returned to baseline or Grade  $\leq 1$  severity (or, at the investigator discretion, Grade  $\leq 2$  if not considered a safety risk for the patient).

If a treatment delay results from worsening of hematologic or biochemical parameters, the frequency of relevant blood tests should be increased as clinically indicated.

If these conditions are met within 2 weeks of treatment interruption or cycle delay, PF-06840003 dosing may be resumed. Refer to Section Dose Reductions for AEs requiring dose reduction at the time of treatment resumption.

If these conditions are not met, treatment resumption must be delayed up to a maximum of 2 weeks. If these parameters have not been met after 2 weeks of dosing interruption, or 2 weeks of new cycle delay, permanent discontinuation of treatment with PF-06840003 should be considered. Treatment resumption for patients recovering from treatment-related toxicity after >2 weeks of treatment interruption or cycle delay may be considered only if the patient is deemed to be deriving obvious clinical benefit per the investigator's best medical judgment and needs to be agreed between the investigator and the sponsor.

If a treatment interruption continues beyond Day 28 of the current cycle, then the day when treatment is restarted will be counted as Day 1 of the next cycle.

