**Non-hematologic:**

- Any toxicity attributable to PF-06840003 that results in administration of less than 80% of the planned doses during Cycle 1.
- Grade 4 non hematologic AE.
- Grade 3 AE lasting >7 days despite optimal supportive care.
- Grade 3 CNS AE regardless of duration. CNS AEs are those events listed within the nervous system disorders category in the NCI CTCAE version 4.03.
- Grade 3 QTc prolongation (QTc >500 msec) will be considered a DLT only if persisting after correction of any reversible causes.
- Concurrent aspartate aminotransferase (AST) or alanine aminotransferase (ALT) >3 x upper limit of normal (ULN) and total bilirubin >2 x ULN.

The following AEs will not be considered as DLTs:

- Isolated Grade 3 or 4 laboratory abnormalities that are not associated with clinical sequelae or are corrected to Grade  $\leq$ 1 with supplementation/appropriate management within 72 hours of their onset.

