**Table 3. Dose Modifications for Investigational Product-Related Toxicity**

| Toxicity        | Grade 1                          | Grade 2                          | Grade 3  | Grade 4   |
|-----------------|----------------------------------|----------------------------------|--|---|
| Non-hematologic | Continue at the same dose level. | Continue at the same dose level. | Withhold dose until toxicity is Grade $\leq 1$ , or has returned to baseline, then resume treatment at the same dose level or reduce the dose by 1 level at the discretion of the investigator*. | Withhold dose until toxicity is Grade $\leq 1$ , or has returned to baseline within 14 days, then reduce the dose by 1 level and resume treatment, or discontinue at the discretion of the investigator*. |
| Hematologic     | Continue at the same dose level. | Continue at the same dose level. | Withhold dose until toxicity is Grade $\leq 1$ , or has returned to baseline, then resume treatment at the same dose level**.  | Withhold dose until toxicity is Grade $\leq 1$ , or has returned to baseline, then reduce the dose by 1 level and resume treatment or discontinue at the discretion of the investigator**.                |

\* Nausea, vomiting, or diarrhea must persist at Grade 3 or 4 despite maximal medical therapy to require dose modification.

\*\* Cycle will not be extended to cover for the missing doses.

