#### **7.1.5. (12-Lead) Electrocardiogram**

Electrocardiogram (ECG): Triplicate 12-lead (with a 10-second rhythm strip) tracing will be used for all ECGs, except the screening assessment. It is preferable that the machine used has a capacity to calculate the standard intervals automatically. At each time point (see the [Schedule of Activities](#)), 3 consecutive ECGs will be performed at approximately 2 minutes apart to determine the mean QTcF interval. If the mean QTcF is prolonged ( $>500$  msec, ie, CTCAE Grade  $\geq 3$ ), then the ECGs should be re-evaluated by a qualified person at the site for confirmation as soon as the finding is made, including verification that the machine reading is accurate. If manual reading verifies a QTcF of  $>500$  msec, immediate correction for reversible causes (including electrolyte abnormalities, hypoxia and concomitant medications for drugs with the potential to prolong the QTcF interval) should be performed. In addition, repeat ECGs should be immediately performed hourly for at least 3 hours until the QTcF interval falls below 500 msec. If QTcF interval reverts to less than 500 msec, and in the judgment of the investigator(s) and sponsor is determined to be due to cause(s) other than investigational product, treatment may be continued with regular ECG monitoring. If in that timeframe the QTcF intervals rise above 500 msec the investigational product will be held until the QTcF interval decreases to 500 msec. Patients will then restart the investigational product at the next lowest dose level. If the QTcF interval has still not decreased to  $<500$  msec after 2-weeks, or if at any time a patient has a QTcF interval  $>515$  msec or becomes symptomatic, the patient will be removed from the study. Additional triplicate ECGs may be performed as clinically indicated.

Prior to concluding that an episode of prolongation of the QTcF interval is due to investigational product, thorough consideration should be given to potential precipitating factors (eg, change in patient clinical condition, effect of concurrent medication, electrolyte disturbance) and possible evaluation by specialist.

If patient experiences a cardiac or neurologic AE (specifically syncope, dizziness, seizures, or stroke), an ECG (triplicate) should be obtained at the time of the event.

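### Section 5.4.3 and Table 3 set different recovery levels for restarting after a toxicity hold, and the hold triggers also differ; in Cycle 1 this can decide the under-80%-of-doses DLT item.

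*Protocol*

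**What the plan says.** **Recovery before restart.** Section 5.4.3 says that re-treatment after a toxicity hold, or at the start of a new cycle, "may not occur until all of the following parameters have been met". The non-hematologic parameter is baseline or Grade 1 or below in "severity (or, at the investigator discretion, Grade" 2 or below, provided the investigator sees no safety risk. The section adds that dosing may resume if its conditions are met within two weeks. Table 3, for Grade 3 and Grade 4 toxicity of both classes, reads "Withhold dose until toxicity is Grade $\leq 1$ , or has returned to baseline". Its investigator discretion concerns the restart dose or discontinuation, not the recovery level. Section 5.4.2 names Section 5.4.3 as the place where restart criteria are found and refers dose-reduction questions to Section 5.4.4, where Table 3 sits.

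**Trigger for a hold.** Section 5.4.2 interrupts treatment for any potentially related Grade 3 or 4 toxicity and for "Intolerable Grade 2 toxicity despite supportive care". Table 3 continues dosing at every Grade 2 toxicity. Its footnote says that nausea, vomiting or diarrhea "must persist at Grade 3 or 4 despite maximal medical therapy to require dose modification". Section 5.4.1 lists interruption within a cycle as one form of dose modification.

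**Link to the Part 1 primary endpoint.** Section 3.2 counts as a DLT any attributable toxicity that "results in administration of less than 80% of the planned doses during Cycle 1". Section 5.4.2 says that doses omitted for toxicity are not replaced within the cycle.

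**The concern.** A patient whose Grade 3 non-hematologic event has improved to Grade 2 may restart under one passage and must stay off drug under the other. Two sites could treat the same patient differently and both be following the protocol.

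This also reaches the dose-escalation data. Held doses are lost, and losing enough of them in Cycle 1 to an attributable toxicity is itself a DLT. The passage a site follows can therefore decide whether the same clinical course is scored as a DLT. Cohorts are 2 to 4 patients, so one DLT more or less can change the Table 2 decision.

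**Working it through.** **1. The passages side by side**

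| Situation | Sections 5.4.2 / 5.4.3 | Table 3 |
|---|---|---|
| Grade 3 non-hematologic, now Grade 2 | Restart allowed at investigator discretion | Still withheld |
| Intolerable Grade 2 | Interrupt | Continue; no reference to the exception |
| Grade 3 or 4 nausea, vomiting or diarrhea, potentially related, not yet shown to persist despite maximal therapy | Interrupt | Dose modification not required |

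**2. The plan's own decision cells.** The inputs are the Beta(0.5, 0.5) prior and the cut points 0.225 and 0.325 from Section 9.2.1. For x DLTs in n patients the posterior is Beta(0.5 + x, 0.5 + n − x). The unit probability mass of an interval is its posterior probability divided by its length, and the largest of the three decides.

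- n = 4, x = 0: 3.820 (under), 0.734 (proper), 0.099 (over), so escalate.
- n = 4, x = 1: 1.809, 1.905, 0.596, so stay.

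Both agree with Table 2. All Table 2 cells for n = 2 to 8 reproduce if U is taken as posterior P(DLT rate > 0.275) > 0.95. That cut-off is an assumption, because the documents give none.

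**3. Missed doses that trigger the under-80% item.** A cycle is 28 days, so there are 28 planned doses on QD and 56 on BID. The share given is (planned − missed) / planned.

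- QD: 0.80 × 28 = 22.4. Five missed: 23/28 = 82.1%, not a DLT by this item. Six missed: 22/28 = 78.6%, a DLT.
- BID: 0.80 × 56 = 44.8. Eleven missed: 45/56 = 80.4%. Twelve missed (six days): 44/56 = 78.6%.

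On either schedule a six-day hold crosses the line and a five-day hold does not.

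**4. When the two recovery rules disagree.** Let an attributable, non-CNS, non-hematologic clinical event spend a days at Grade 3 and then b days at Grade 2 before reaching Grade 1, all within Cycle 1, with no other missed doses and a baseline of Grade 1 or below. Restart under the 5.4.3 discretion misses a days; restart under Table 3 misses a + b. The scoring differs when a ≤ 5 and a + b ≥ 6. The separate item for Grade 3 lasting more than 7 days is then not met.

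Illustration with a = 3, b = 4, QD:

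- Section 5.4.3 with discretion: (28 − 3)/28 = 25/28 = 89.3%, no DLT.
- Table 3: (28 − 7)/28 = 21/28 = 75.0%, DLT.

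**5. What one DLT does in Table 2**

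- 0/3 (E) becomes 1/3 (S).
- 1/3 (S) becomes 2/3 (D).
- 1/6 (E) becomes 2/6 (S).

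Not every added DLT matters: 0/6 and 1/6 are both E.

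**6. The trigger conflict in the same terms.** If a site interrupts for intolerable attributable Grade 2 toxicity under Section 5.4.2 and the hold reaches six days, the under-80% item is met. If it continues under Table 3, no dose is missed and the item is not met.

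**The case against.** The strongest reply is that the documents can be read together. Both passages have the same default of baseline or Grade 1, and part only when the investigator uses discretion. Section 5.4.3 is worded as a minimum, so a site that waits for Table 3's level also satisfies the non-hematologic item. Section 5.4.2 points to 5.4.3 for restart, and the Grade 2 allowance has a separate use at the start of a new cycle. This narrows the conflict but does not remove it. Section 5.4.3 also says dosing may resume once its conditions are met, Table 3 states its own recovery level, and neither is made subordinate.

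On the trigger, the reply is stronger. Section 5.4.4 recommends no specific adjustment for Grade 1 or 2, preserves medical judgment, and deals separately with recurrent and intolerable Grade 2. Table 3 can then be read as the default, with a stated exception elsewhere. The gastrointestinal footnote can likewise be read as a specific exception to a general rule. What stands is that Table 3 does not refer to the Grade 2 exception, and Section 5.4.2 does not mention the footnote.

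A reader might go further in three ways that the documents do not support:

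- **That the QTcF rule is a third general recovery level.** Section 7.1.5 says "the investigational product will be held until the QTcF interval decreases to 500 msec", but this applies to one event. Comparing it with Table 3's Grade 1 needs CTCAE limits that the documents do not print.
- **That the ANC and platelet thresholds in Section 5.4.3 contradict Table 3's hematologic row.** That also needs unprinted grade limits.
- **That missed days decide Cycle 1 DLTs in general.** They decide one item. Grade 4 non-hematologic events, Grade 3 CNS events and Grade 3 events lasting over 7 days can count however many doses are missed.

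Finally, the course in the illustration is invented and nothing in the documents gives its frequency. Attribution and alternative explanations remain judgments under any wording, and the sponsor and investigators discuss adverse events at each dose level (Section 9.8).

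**Conclusion.** The contradiction on recovery level is in the current text and needs no outside source: Section 5.4.3 permits restart at Grade 2 by discretion, Table 3 does not, and no passage ranks them. The difference in hold triggers is secondary and partly explained by Section 5.4.4.

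The consequence is real but confined to the under-80% item. On either dosing schedule it turns on whether the hold reaches six days, and the two readings give opposite scores when Grade 3 lasts at most five days and Grade 3 plus Grade 2 together last at least six. One changed score can move a small cohort between escalate and stay, or between stay and de-escalate. This assumes an attributable, non-CNS, non-hematologic event that is not an isolated laboratory abnormality excluded by Section 3.2, a hold wholly inside Cycle 1, and discretion actually exercised. How often this would happen cannot be estimated from the documents. The point should be corrected because it affects both patient handling and the Part 1 primary endpoint, but it does not invalidate the escalation design.

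**What to change.** Reconcile Sections 5.4.2, 5.4.3, 5.4.4 and Table 3 with its footnote, so that each toxicity class has one hold trigger and one recovery criterion. Have Table 3 refer to that criterion instead of stating its own. Identify the event-specific rules, QTcF in Section 7.1.5 and cerebral edema in Section 5.7.3, as exceptions. The under-80% item in Section 3.2 would then rest on one hold-and-restart rule across sites and dose levels, although attribution would remain a judgment.

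Which trigger and which recovery level apply is for the sponsor's clinicians; nothing here favors either. No separate SAP change is needed, because SAP Section 6.1 defers to the protocol for the DLT definition. The cost is a protocol wording amendment, with no added patients or procedures.
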